Participants will be monitored for exercise-associated events (hypo- and hyperglycemia, diabetic ketoacidosis, other health risks) as detailed in the Data and Safety Monitoring Plan (Sect 8.7). In brief, a research staff member will daily review each participant's CGM data, fingerstick glucose tests, ketone tests, exercise start times, and diary records of hypoglycemia and other clinical events (see Data and Safety Monitoring Plan "Tracking" section) each of the first 14 days of the trial for each participant. Instances of severe hypoglycemia, diabetic ketoacidosis, a missed ketone test, or other clinical event will result in immediate discontinuation of exercise until a physician has alerted the participant and the participant's primary diabetes care provider to the issue and developed a prevention strategy, consulting with the primary diabetes care provider as needed. For instances of a missed test, physician contact can be replaced initially by research assistant contact to query symptoms and troubleshoot testing procedures, followed by physician contact if symptoms were present.

The principal investigator [name] and a study physician (Drs. [name] or [name]) will review the above data plus carbohydrate and insulin dosing around exercise, every 2 weeks during the clinical trial. Participants exhibiting patterns confirmed by the physician to be indicative of problematic exercise-induced hypo- or hyperglycemia will be alerted to the issue and referred to their diabetes care provider for follow-up (all patients will submit provider information to the study team at study start). [name] will join at least every other occurrence of these meetings (i.e., at least every 4 weeks) and provide a second review of [name] medical management decisions. Participants will be trained in allowing their provider to access their CGM data. Mild hypoglycemia will not be exclusionary since such individuals are in high need of exercise intervention. Any day-to-day decisions about clinical care, including adjustment of insulin dosing or CGM target ranges will be made by the participant's provider, not the study physicians. Clinical providers will not monitor CGM in real-time.

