Severe hypoglycemia will be defined as any blood glucose level resulting in symptoms which require outside intervention to control (including but not limited to confusion and loss of coordination). Severe hyperglycemia will be defined as blood glucose >500mg/dL, presence of urine ketones or other signs and symptoms of diabetic ketoacidosis (including but not limited to weakness and fatigue, confusion, shortness of breath). Patients will be asked to contact emergency services should these events occur. Specifically, Yale-affiliated patients with T1D have access to a 24-hour hotline with access to nurse and/or physician advice or can choose to call 911. Non-Yale-affiliated patients will be asked to call 911 or contact their providers' after-hours staff (all patients will submit provider information to the study team at study start). The study team will be notified of the event within 24 hours via daily diaries; moreover all participants will have the PI's direct contact information should they choose to contact him earlier by phone or email. Our team will then notify the patient's primary diabetes provider (if not already notified) and all study-related exercise will be suspended until patient receives further advice from their diabetes provider regarding next steps which may include modified exercise routines or suspension of the study altogether. All serious adverse events such as severe hypoglycemia and hyperglycemia will be reported to the PI verbally within 24 hours of study staff being notified and to university's IRB committee in writing within 5 business days. In the case of >1 episode of severe hypoglycemia or 1 episode of diabetic ketoacidosis not closely related to pump site failure, the participant will be removed from the study and referred to their diabetes care provider for follow-up.

**Exercise-related injuries:** Exercise may cause muscle soreness/pain, muscle strain, cardiovascular events, and tiredness during or after the activity.

The probability and magnitude of such injuries varies based upon factors such as the individual participant's fitness level and the difficulty of the exercise routines. Our previous pilot studies (sect. 1.2) had no injuries or muscle strains. The American Heart Association Scientific Statement notes that the frequency of exercise-related out-of-hospital cardiac arrest among the general population ages 35-90yr was measured at 3.0 per 100,000 person-years.

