# **Tracking**

A. Daily monitoring during first 2 weeks for ketoacidosis, severe hypoglycemia, and other health risks associated with exercise:

We will detect any diabetic ketoacidosis or severe hypoglycemia within 24hr and suspend exercise until a personalized preventive strategy can be formed. To achieve this level of monitoring, a research assistant will monitor daily the biometric dashboard which contains Bluetooth-captured glucose, ketones, and exercise start/stop times. Safety signals include any of the following during or within 1hr of exercise: 1) Diabetic ketoacidosis (glucose ≥270 mg/dL + ketones ≥1.0 mmol/L), 2) Possible diabetic ketoacidosis (glucose ≥270 mg/dL and failure to test ketones), and 3) Possible severe hypoglycemia (glucose <55 mg/dL). Research staff will respond to each of these events within 24hr of its occurrence by informing the participant to immediately suspend the exercise program (app account will be suspended) until the participant has been contacted by a study physician. The physician will alert the participant and the participant's primary diabetes care provider to the issue and develop a prevention strategy, consulting with the primary diabetes care provider as needed. The exercise suspension will then be lifted, unless the participant has met the protocol's stoppage criteria (>1 episode of severe hypoglycemia, 1 episode of diabetic ketoacidosis not closely related to pump site failure).

In the event of the "possible" occurrences (#2, #3), physician contact can be replaced initially by research assistant contact to query symptoms. Then, if possible diabetic ketoacidosis is supported by the participant reporting symptoms, or possible severe hypoglycemia is supported by the participant reporting altered mental and/or physical status requiring assistance from another person for recovery, physician contact will be required as in paragraph #1 above.

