# **Steps to Minimize**

Among enrolled subjects, steps will be taken to minimize risks of hypoglycemia and hyperglycemia as detailed in section 2.2, "Protection against Risks". Briefly, these include

August 13, 2024 Version #7

instructions to participants regarding safe blood glucose testing habits, regular tracking of hypoglycemia and hyperglycemia as described above, blood glucose monitoring review by Drs. [name] and [name] every 2 weeks with clinical referrals by [name] as appropriate, second check of [name] medical management decisions by [name] at least every 4 weeks, and routine clinical support. Regarding non-glycemic medical issues related to older age (e.g., angina history), [name] will be available for consultations.

Participants will be instructed to call the Yale 24-hour access to nurse and/or physician consultation or 911 if they have any instances of severe hypoglycemia, diabetic ketoacidosis, or other severe clinical event. Non-Yale-affiliated participants will be required to submit information regarding their providers and will be instructed to call 911 if they do not have access to 24-hour consultation and experience an adverse event. Any such instances noted on participant diary surveys will be reviewed by our study team and forwarded to their diabetes provider. Patients will be instructed to suspend exercise until they have a chance to connect with their provider who will then determine the next steps regarding resumption of exercise and ongoing mobile application usage. Any day-to-day decisions about clinical care including adjustment of insulin doses or CGM target ranges will be made by the participant's provider, not the study physicians.

These protocols have been utilized by Drs. [name], [name], and [name] over four prior exercise clinical trials among youth and adults with T1D that had no instances of severe hypoglycemia or diabetic ketoacidosis (HIC #s 1605017843, 2000025992, 2000030105, 2000033736).

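### In the two-week daily monitoring, the study physician's strategy alone can end an exercise suspension that two other provisions hold for the participant's own diabetes provider

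*Combined protocol and SAP*

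**What the plan says.** Four provisions bear on when exercise may restart after a serious glycemic event.

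- **Section 8.7, Tracking, part A.** After a safety signal the app account is suspended. The study physician alerts the participant and the participant's diabetes provider, and is to "develop a prevention strategy, consulting with the primary diabetes care provider as needed. The exercise suspension will then be lifted, unless the participant has met" one of the stoppage criteria. For the two signals labelled possible events, "physician contact can be replaced initially by research assistant contact to query symptoms"; physician contact becomes mandatory only if the participant's answers support the event. A further paragraph, on clinical events reported in the morning survey that may be exercise-related, repeats the release by the study physician.
- **Section 2.2, Hypoglycemia.** Exercise stops "until a physician has alerted the participant and the participant's primary diabetes care provider to the issue and developed a prevention strategy", with the provider consulted only where necessary. For a missed ketone test the research assistant may make contact first, "followed by physician contact if symptoms were present".
- **Section 2.2, Severe hypoglycemia and hyperglycemia.** "Severe hyperglycemia will be defined as blood glucose >500mg/dL, presence of urine ketones or other signs and symptoms of diabetic ketoacidosis". After a severe event, "all study-related exercise will be suspended until patient receives further advice from their diabetes provider regarding next steps".
- **Section 8.7, Steps to Minimize.** After severe hypoglycemia, ketoacidosis or another severe clinical event, the participant stops exercising until in touch with the provider, "who will then determine the next steps regarding resumption of exercise and ongoing mobile application usage".

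**The concern.** Tracking A makes the provider's input optional and then lifts the hold. The severe-event paragraph of section 2.2 and Steps to Minimize make that input the condition for restarting. Staff have to act on a signal within 24 hours, in a study that section 2.2 rates as greater than minimal risk. Someone following Tracking A to the letter can reopen the app before the provider has said anything, contrary to the other two provisions. For one type of reading, the research-assistant route can end with no clinician contacted at all. What is at stake is consistent handling of participants after a severe event.

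**Working it through.** There is no figure to reproduce; the check is to apply each rule to the same event.

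1. **Which events need a release rule?** The stoppage criteria (section 2.2, section 6.5, Tracking A) are more than one severe hypoglycemia, or one ketoacidosis not closely related to pump-site failure. A first severe hypoglycemia is one episode, and 1 is not more than 1. A ketoacidosis closely tied to a failed pump site is exempt by definition. Both participants stay in, so something must say when they restart.

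2. **Where does severe hyperglycemia enter Tracking A?** It is not named there. The relevant signals, during or within 1 hour of exercise, are glucose of at least 270 mg/dL with ketones of at least 1.0 mmol/L (ketoacidosis), or glucose of at least 270 mg/dL with ketones untested (possible ketoacidosis). Since 500 > 270, any reading above 500 mg/dL in that period with no ketone test is both severe hyperglycemia under section 2.2 and only a possible event under Tracking A.

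3. **The rules side by side:**

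| Event in the monitoring period | Section 8.7, Tracking A | Section 2.2, severe events | Steps to Minimize |
|---|---|---|---|
| First severe hypoglycemia | Lifted after study physician's strategy | Held for provider's advice | Provider decides |
| Ketoacidosis closely tied to failed pump site | Lifted after study physician's strategy | Held for provider's advice | Provider decides |
| Glucose >500 mg/dL around exercise, ketones untested, no symptoms | Research-assistant contact; no physician or provider contact required | Held for provider's advice | Not named as such |
| Glucose >500 mg/dL, ketones tested and <1.0 mmol/L | Not a dashboard signal; reaches the study-physician release only if survey-reported and possibly exercise-related | Held for provider's advice | Not named as such |

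4. **Is one rule given priority?**
   - By section: no. Section 2.2 contains the provider rule and a physician-based hold; section 8.7 contains both release rules. The Hypoglycemia paragraph refers forward to 8.7, and Steps to Minimize refers back to 2.2. The overview of 8.7 says only that the monitoring plan follows the approved protocol.
   - By detection route: no. The Hypoglycemia paragraph puts sensor data, ketone tests and diary records in one daily review.
   - By period: no. Nothing confines the provider rule to the time after the daily monitoring.
   - By the sentence reserving day-to-day care to the provider: no. Its examples are insulin dosing and sensor target ranges, and Steps to Minimize deals with resumption of exercise separately.

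5. **Can both rules be satisfied?** Yes. Tracking A sets no deadline for the strategy, so a physician who first obtains the provider's advice meets every provision. But no provision requires that order.

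**The case against.** The best defence is that these are minimum conditions that add up. That is right for the Hypoglycemia paragraph of section 2.2: it says how long exercise must at least be withheld, speaks of a physician without specifying a study physician, and never says the hold then ends. A reader might count it as a second provision letting exercise resume, but it is compatible with either rule. The defence fails for Tracking A, which goes on to lift the suspension with one stated exception, the stoppage criteria. Its survey paragraph does the same.

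It can also be said that reopening an app account does not cancel the instruction given to the participant in Steps to Minimize, and that Tracking A does have the provider alerted. Both are true. But being alerted is not the same as advising, and Steps to Minimize gives the provider the decision on app use, which Tracking A suspends and restores.

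For glucose above 500 mg/dL, one may answer that the possible-event step is only a screen and that the specific severe-event rule applies as well. That is a sensible reading, but the text leaves staff to infer it.

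Other safeguards limit the consequence. An endocrinologist reviews glucose and ketone data every 2 weeks (Tracking, part B). Clearance can be revoked at any time (section 8.7, Exercise-related injuries). Researchers may withdraw a participant whose interest is not served by continuing (section 6.5). None of these ranks the two rules. Finally, the exercise data monitoring appendix (22b) and the internal procedure manual are not in the supplied text and might set the order of contacts.

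**Conclusion.** The inconsistency is real and minor. It is clear for a first severe hypoglycemia and for a ketoacidosis closely tied to a failed pump site. For severe hyperglycemia it arises in Tracking A only when the reading is also one of that section's signals, or through the survey paragraph. The untested, symptom-free reading above 500 mg/dL matters most, because the rules then differ on whether any clinician is required. This takes the section 2.2 definition as a list of alternatives, so that the glucose value alone suffices.

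Three stronger inferences are not supported:

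- **That the rules cannot both be followed.** One sequence of contacts satisfies all of them.
- **That every severe hyperglycemia is released without the provider.** A reading above 500 mg/dL with ketones tested below 1.0 mmol/L is not a dashboard signal.
- **That participants restart unsupervised as a rule.** The study-physician and provider routes are both supervised.

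Events should be rare: sections 2.2 and 8.7 report no severe hypoglycemia or ketoacidosis in four earlier exercise trials, though they give no count of readings above 500 mg/dL. No endpoint or analysis is affected. The start day of the two-week window is a separate question on which this conclusion does not depend. That no precedence is stated holds for the supplied text only.

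**What to change.** In both release paragraphs of section 8.7, Tracking A (dashboard signals and survey-reported events), with matching wording in the Hypoglycemia paragraph of section 2.2, state the following. After severe hypoglycemia, diabetic ketoacidosis, severe hyperglycemia as section 2.2 defines it, or another severe clinical event under Steps to Minimize, the suspension is lifted only when two conditions are met: the study physician's prevention strategy is in place, and the participant's diabetes provider has advised on resumption.

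Limit the research-assistant-only route to possible signals that do not meet the severe-event definitions of section 2.2, so that a glucose above 500 mg/dL without a ketone test leaves that route. Keep the primary-care clearance rule for symptoms and injuries (section 2.2, Exercise-related injuries; section 8.7, Tracking, part C) as it is.

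The combined rule joins two conditions the protocol already states separately. Other rules would also remove the conflict; this one drops neither safeguard. The cost is a wording amendment in three places, with the ethics approval that section 9.1 requires, and a possibly longer suspension in rare cases. The documents give no basis for estimating how much longer.

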# B. Biweekly monitoring for mild hypo- or hyperglycemia:

Data on glucose, ketones, exercise timing, carbohydrate consumption, and insulin will be compiled by a research assistant and reviewed for each subject every 2 weeks at study team meetings by the principal investigator [name] and one of the study endocrinologists Drs. [name] or [name]. The data will firstly be reviewed for patterns indicative of mild hypo- or hyperglycemia related to exercise. The most common are failure to take adequate carbohydrate supplementation relative to starting glucose values, nocturnal hypoglycemia following exercise, failure to adequately reduce pre-exercise bolus insulin, or starting exercise with elevated glucose values (Table 3, Sect 6.1.1). Safety issues will be noted and communicated to participant. Participant will be referred to their diabetes care provider if insulin dose adjustments are needed. The data will secondly be reviewed for adverse events. The study timetable has been set so that no more than 11 participants are active at one time, making this auditing manageable. Adverse events will be defined as severe hypoglycemia (an event that required assistance from another person to administer carbohydrate, glucagon,

August 13, 2024 Version #7

or other resuscitative actions), diabetic ketoacidosis, and serious adverse events regardless of causality. [name] will join at least every other occurrence of these meetings (i.e., at least every 4 weeks) and provide a second review of [name] medical management decisions. [name] is a world expert in CGM for T1D glycemic management in adult patients 18-25 years old, whose glycemic patterns are similar to those 30-65 years old. As a preeminent CGM authority he frequently advises adult endocrinologists on CGM issues. Regarding non-glycemic medical issues related to older age (e.g., angina history), [name], an adult endocrinologist at the University of Maryland and previous collaborator of [name] ([name] manuscripts and [name] own clinical trial NCT04800471), will be available for consultations. Participant histories will be de-identified prior to [name] viewing and commenting.

# C. Weekly monitoring for elevated blood pressure (BP) and symptoms

The protocol also includes tracking of blood pressure (BP) so that participants developing uncontrolled accelerated hypertension can be removed from the study and referred for follow-up. Weekly tracking protocols are based upon [name] dissertation and a prior exercise clinical trial conducted in the same laboratory overseen by [name], Chief of Cardiology, Hartford Hospital. In those trials, participants with pre- to stage 1 hypertension safely performed moderate to maximal exercise. Those trials utilized office BP criteria of uncontrolled accelerated hypertension (systolic > 160 mmHg and/or diastolic >100 mmHg) for study exclusion which are cutoffs where consensus guidelines recommend more careful monitoring. We will use these cutoffs. The specific procedures are below:

BP will be checked by all participants at all weekly visits (visits 2-10) by standard home monitoring procedures. Briefly, we will take the average of 2 brachial artery measurements after ≥12 hours abstention from acute blood pressure confounders (exercise, caffeine, alcohol, tobacco, nicotine) and ≥5 minutes of quiet rest using the Omron BP7350 (Omron Healthcare), which includes a rigid cuff that minimizes fitting errors. If the measurements differ by >5 mmHg, then a third will be taken and the closest two will be averaged. In the event of a result meeting the home BP monitoring criteria for uncontrolled accelerated hypertension (systolic >145 mmHg and/or diastolic >90 mmHg), the result will be faxed to the participants' primary diabetes healthcare provider as a possible early indicator of true uncontrolled accelerated hypertension. In the event of a result meeting uncontrolled accelerated hypertension (systolic >160 mmHg and/or diastolic >90 mmHg) the participant will be withheld from exercise participation until BP can be reassessed at least one day later. In the event of a second occasion meeting these values, the participant will be removed from the study and referred to their healthcare provider for follow-up.

The research assistant will ask the participant if they are having any of the symptoms overviewed on the consent form or any other injuries that could be made worse by exercising. In the event of positive responses, exercise physiologist (EP) [name] will contact them to ask follow-up questions, following protocols from the American College of Sports Medicine, to determine if they are indicative of pathology. If they are, [name] will report the episode to study physician [name] and the participant's own PCP and suspend the participant's exercise participation unless receiving PCP clearance to continue. For complaints that are musculoskeletal issues that can be temporarily avoided by the EP [name] recommending GlucoseZone videos that avoid the injured area, then such videos can be continued without PCP clearance.

# **Steps to Minimize**

Among enrolled subjects, steps will be taken to minimize risks of hypoglycemia and hyperglycemia as detailed in section 2.2, "Protection against Risks". Briefly, these include

August 13, 2024 Version #7

instructions to participants regarding safe blood glucose testing habits, regular tracking of hypoglycemia and hyperglycemia as described above, blood glucose monitoring review by Drs. [name] and [name] every 2 weeks with clinical referrals by [name] as appropriate, second check of [name] medical management decisions by [name] at least every 4 weeks, and routine clinical support. Regarding non-glycemic medical issues related to older age (e.g., angina history), [name] will be available for consultations.

Participants will be instructed to call the Yale 24-hour access to nurse and/or physician consultation or 911 if they have any instances of severe hypoglycemia, diabetic ketoacidosis, or other severe clinical event. Non-Yale-affiliated participants will be required to submit information regarding their providers and will be instructed to call 911 if they do not have access to 24-hour consultation and experience an adverse event. Any such instances noted on participant diary surveys will be reviewed by our study team and forwarded to their diabetes provider. Patients will be instructed to suspend exercise until they have a chance to connect with their provider who will then determine the next steps regarding resumption of exercise and ongoing mobile application usage. Any day-to-day decisions about clinical care including adjustment of insulin doses or CGM target ranges will be made by the participant's provider, not the study physicians.

These protocols have been utilized by Drs. [name], [name], and [name] over four prior exercise clinical trials among youth and adults with T1D that had no instances of severe hypoglycemia or diabetic ketoacidosis (HIC #s 1605017843, 2000025992, 2000030105, 2000033736).

